9.3.2 Fresh Tissue Biopsies

Enrolled participants with accessible disease will undergo required paired research biopsies at baseline and on treatment and an optional biopsy at progression. In the case of retreatment, there may be additional biopsies performed at progression timepoints. Tissue collected from these biopsies will be used in accordance with section 9.3.3.

9.3.3 Potential Tissue Assays

Assay 1: Tumor infiltrating lymphocyte (TIL) percentage and determination of lymphocyte predominant breast cancer (LPBC)

- Paraffinized, hematoxylin and eosin-stained slides taken from 1-2 tissue planes will be derived from each biopsy and will be reviewed by certified pathologists. In the research setting, all cases are reviewed by two pathologists and any discordant results resolved by consensus review. The extent of lymphocytic infiltrate in tumor tissue will be assessed, and stromal TIL percentage will be determined. More detailed guidelines for the quantification of stromal TILs in breast cancer can be found in the recommendations from the International TILs Working Group.⁸⁸
- After assessment of the TIL percentage, the pathologists will categorize the specimen as lymphocyte predominant breast cancer (LPBC), defined as a tumor that contains >60% stromal lymphocytes, or non-LPBC.

Assay 2: Immunohistochemistry and immunofluorescence assays

- Tissue will be collected and fixed by 10% neutral buffered formalin overnight, dehydrated, and paraffin embedded. Four micrometer-thick sections will be cut. The paraffin blocks and unstained slides will be stored at room temperature. Immunohistochemical staining will be performed in the Center for Immuno-Oncology Pathology Core at Dana-Farber/Harvard Cancer Center (DF/HCC) Specialized Histopathology Core.
- Unstained slides from a metastatic site or newly acquired biopsy may be sent to BWH Pathology, Yale Cancer Center, [REDACTED] or Ventana for exploratory assessment of Trop-2 expression and other biomarkers.
- Formalin-fixed, paraffin-embedded (FFPE) tumor slides will be prepared and H&E stained for assessment of TIL in pre- and post-treatment tumor samples. Subsets of different immune populations (effector/memory CD8 cells, T regulatory cells, dendritic cells, tumor

associated macrophages, and Tie-2 expressing monocytes (TEM)) will be identified using immunohistochemical (IHC) and/or immunofluorescence (IF) staining on FFPE tumor slides. Cyclic immunofluorescence (CyCIF) at Harvard Medical School may also be utilized to define immune cell subpopulations and single cells with this highly multiplexed immunostaining method.

- Central PD-L1 IHC testing may also be performed on the tumor tissue research biopsies collected on study. Up to five FFPE unstained slides (4-5 micron thickness) may be sent to DLS/Qualtek for central PD-L1 testing, which will occur retrospectively. This will allow characterization of changes in PD-L1 expression with exposure to therapy and will also enable comparison of PD-L1 results between metastatic research tumor biopsies and archival tumor samples (Section 9.1 and 9.3.1).

Testing for PD-L1 positivity will be performed by Discovery Life Sciences (DLS)/QualTek Molecular Laboratories. PD-L1 protein expression will be determined by using the anti-PD-L1 antibody clone IHC 22C3 PharmDx commercial kits (Agilent). The specimen will be considered PD-L1-positive if CPS ≥ 1 .

- Investigators at our institution have developed IHC staining on paraffin embedded tissues for PD-L1, PD-L2, TIM-3, and LAG-3 through our center for Immuno-Oncology Pathology Core ([name] [name], Core Director). PD-L1 IHC has recently been established in a CLIA approved laboratory and the remaining assays for CLIA laboratory conduct are being finalized.

These investigators have published the methods, protocols, and data establishing the sensitivity and specificity of IHC staining assays using the monoclonal antibodies recognizing PD-L1 (CD274, B7-H1, antibody clone 7G11, generated in the lab of [name], DFCI) and PD-L2 (CD273, B7-DC, clone 9E5, generated in the laboratory of [name], DFCI).^{89,90}

Tumor and immune cell expression of PD-L1 will be evaluated at different cut-off points (i.e. 1%, 5%, 10%, 50%). All IHC stained slides will be evaluated by a pathologist and H-scores will be reported. A subset of slides will be reviewed by a second pathologist to ensure concordance of interpretation.

The semi-quantitative scoring for this study is in accordance with those published previously and as described above, will include scores for both the neoplastic and non-neoplastic cells within the tumor microenvironment. Data derived from pathologist visual scoring (semi-quantitative, but with increased specificity for delineating neoplastic and non-neoplastic cells) and pathologist-assisted, automated scoring (quantitative, but without accurately delineating neoplastic and non-neoplastic cells) for each marker of interest will be assessed for its clinical value.

- FFPE tumor slides will also be assessed by IHC and/or IF assays for other markers, including MHC class I and II markers (HLA-ABC, HLA-DR) and dendritic cell markers (CD11c, CD1c, CD123), as deemed appropriate and informative based on the literature at

the time of correlative science performance.

Assay 3: Bulk and Single-Nucleus RNA Sequencing

RNA analysis may be performed, and tissue for RNA analysis will be stored, in the DFCI-T-Hub. Messenger RNA (mRNA) expression within tumor biopsy specimens may be assessed using the most current and informative methodologies at the time that correlative science is performed on all specimens. NanoString signatures and/or whole transcriptome sequencing may be used. Potential genes of interest, based on prior immune profiling of breast tumors include CXCL9, CCL5, CD8ACD80, CXCL13, IGKC, CD21, IDO1, PD-1, PD-L1, PD-L2, CTLA4, and FOXP3.⁹¹

Perou and others have previously shown that within TNBC, exists all of the intrinsic subtypes of breast cancer. Thus, we propose to use the PAM50 algorithm⁹² and the Claudin-low predictor⁹³ in order to determine the intrinsic subtype of each sample. Specifically, using the RNA-seq data, a global normalization step will be performed to adjust the TNBC RNA-seq data obtained in this study relative to the TNBC subset of patients in the TCGA RNA-seq study. Once this normalization is complete, the PAM50 algorithm will be run as described in Parker et al. 2009, and then the Claudin-low predictor will be run as described in Prat et al., thus classifying samples into 1 of 6 intrinsic subtypes. The intrinsic subtype classifications will be tested for associations with disease response to treatment using univariate and multivariate testing in models that include the standard clinical parameters and with models including other genomic predictors.

For a subset of patients who are enrolled at DFCI, single-nucleus RNA sequencing will be performed on biopsies at baseline, on treatment, and, when available, on progression. These studies will determine whether changes in RNA expression signatures specific to tumor and immune cells correlate with treatment response and resistance. These analyses will also investigate whether particular immune cell subsets are enriched in responders compared to non-responders, as suggested by studies in other tumors treated with checkpoint inhibitors. Additional single-cell techniques may be added to the single-cell RNA sequencing, such as cellular indexing of transcriptomes and epitopes by sequencing (CITE-seq), a method that quantifies cell-surface proteins at a single-cell level.⁹⁴

Assay 4: Whole Exome, Whole Genome Sequencing, DNA Methylation

All DNA sequencing will be performed at the Broad Institute; this may include SNP-arrays for germline genomic analyses, as well as exome and/or whole genome sequencing. Tumor biopsy specimens may be assessed using the most current and informative methodologies at the time that correlative science is performed. Potential assays that may be performed on frozen or FFPE metastatic samples and/or FFPE primary samples include:

- Whole Genome sequencing depth of $\geq 40X$ coverage, or Whole Exome sequencing depth of $\geq 500X$ coverage.
- AFFY SNP 6.0, or Illumina SNP arrays for genotypes and DNA copy number changes may be performed.
- DNA methylation: Illumina Infinium 450K methylation arrays.

Previously performed, CLIA-approved NGS panels (i.e., DFCI's Oncopanel) on participants (either from the pre-screening population or the enrolled population) may be requested and utilized in these analyses.

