1 OBJECTIVES

1.1 Study Design

This is a randomized phase 2 open label study of sacituzumab govitecan +/- pembrolizumab for patients with hormone receptor-positive (HR+) / HER2- metastatic breast cancer (MBC). Patients will be randomized in a 1:1 ratio to sacituzumab govitecan (IMMU-132) with pembrolizumab (Arm A) or sacituzumab govitecan alone (Arm B) and will be treated until unacceptable toxicity or progression as defined by RECIST 1.1 criteria.

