3.1 Eligibility Criteria

- 3.1.1 Participants must have histologically or cytologically confirmed invasive breast cancer with unresectable locally advanced or metastatic disease. Participants without pathologic or cytologic confirmation of metastatic disease should have unequivocal evidence of metastasis from physical examination or radiologic evaluation, i.e. visible chest wall disease or metastases on imaging meeting standard radiology criteria (i.e., lymph nodes larger than 1 cm in the short axis diameter).
- 3.1.2 Participants must have HR-positive, HER2-negative breast cancer (ER \geq 1% and/or, PR \geq 1%, HER2-negative per ASCO CAP guidelines) on local pathology review. If a patient has more than one histological result, the most recent sample will be considered for inclusion.
- 3.1.3 Participants must have either progressed on or within 12 months of adjuvant endocrine therapy within the last 12 months or have progressed on at least one line of endocrine therapy for metastatic disease and be considered appropriate candidates for chemotherapy.
- 3.1.4 Participants must have evaluable or measurable disease per RECIST 1.1. See Section 11 for the assessment of measurable disease. For instance, patients with bone only disease will be allowed to participate.
- 3.1.5 Participants must agree to undergo a research biopsy, if tumor is safely accessible, at baseline. Previously collected archival tissue will also be requested, if available, for all participants. A source of archival tumor tissue should be identified at time of registration (see Section 9 for more details). Participants must agree to a mandatory repeat biopsy 3-6 weeks after starting treatment, if tumor is safely accessible.
- 3.1.6 **Prior chemotherapy:** Participants may have received 0-1 prior chemotherapeutic regimens for metastatic breast cancer and must have been off treatment with chemotherapy for at least 14 days prior to study treatment initiation. If a prior chemotherapy was given for less than 1 cycle, it will not be counted as a prior line. No prior irinotecan or topoisomerase I-containing antibody drug conjugates in the metastatic or neo/adjuvant setting are allowed. All toxicities related to prior chemotherapy must have resolved to CTCAE v5.0 grade 1 or lower, unless otherwise specified in 3.1.15, except alopecia can be any grade and neuropathy can be grade 2 or lower.

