9 BIOMARKER, CORRELATIVE, AND SPECIAL STUDIES

All biomarker analyses completed on blood and tissue samples for correlative data will be exploratory.

Prior to Sponsor Amendment 3, the PD-L1 eligibility amendment: All patients who underwent pre-screening for the trial were required to submit an archival tissue sample for central PD-L1 testing. If the participant enrolled on the trial, no additional archival tissue was required.

Additional tissue leftover after central testing will be used for tissue analyses listed in Section 9.3. Any tissue leftover after these analyses have been completed will be banked for future research.

After Sponsor Amendment 3, the PD-L1 eligibility amendment: Central PD-L1 testing will not be required for eligibility. Archival tissue will be requested for all patients for the purposes of retrospective central PD-L1 testing and other exploratory biomarker analyses as described in this section.

In all patients in whom tumor is safely accessible, baseline and on treatment tumor biopsies are required. We plan to use these tissues to perform immune profiling assays, including characterization based on histology (TILs), protein expression, and mRNA expression, as detailed below. We will perform targeted panel (OncoPanel) and whole exome sequencing to determine mutational load and identify specific genomic alterations associated with response. Additionally, we will bank specimens for possible future additional analyses.

Serial blood draws for correlative science are required on this trial; blood draws will be obtained every 9 weeks prior to the infusion of study drugs, at the end-of-treatment visit in patients who go off study for progressive disease, and all efforts will be made to obtain an additional blood draw at the time of progressive disease in patients who went off study for any reason other than progressive disease. On each blood draw, we will perform flow cytometry to characterize protein expression of immune mediators, as detailed below, and additional blood will be banked for future analyses.

Instructions for the collection, labeling and shipment of blood, tissue, and stool samples are outlined below and further detailed in the Lab Manual.

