9.7 Additional Translational Analyses

The above-mentioned analyses may be altered based on novel developments in the field of cancer immune profiling at the time of correlative science. Additional markers or alternative technologies (based on scientific developments and/or novel technologies) may also be used, to explore potential prognostic or predictive candidate markers/panels or markers related to treatment benefit and/or safety, to improve diagnostic tests, or to understand breast cancer biology.

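### The PAM50 step in Section 9.3.3 treats an HR+/HER2- cohort as TNBC and normalizes it to a TNBC reference; how far this harms the subtype calls depends on a normalization the plan does not define

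*Combined protocol and SAP*

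**What the plan says.** Section 3.1.2 sets the population: "Participants must have HR-positive, HER2-negative breast cancer", meaning ER and/or PR of at least 1%. Section 1.1 describes the same population, and the trial has no triple-negative cohort.

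The RNA-sequencing text in Section 9.3.3 (Assay 3) mentions TNBC three times:

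- **Rationale.** Subtyping is proposed because "within TNBC, exists all of the intrinsic subtypes of breast cancer".
- **Study data and reference.** A normalization described only as global is to "adjust the TNBC RNA-seq data obtained in this study relative to the TNBC subset of patients in the TCGA RNA-seq study". This one phrase holds two of the three mentions: the label on the trial's own data and the choice of reference.

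The order of steps is fixed: "Once this normalization is complete, the PAM50 algorithm will be run", followed by the Claudin-low predictor. The output is then used: "The intrinsic subtype classifications will be tested for associations with disease response to treatment", in univariate and multivariate models.

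Two general statements bear on status. Section 9 opens with "All biomarker analyses completed on blood and tissue samples for correlative data will be exploratory". Section 9.7 adds that "The above-mentioned analyses may be altered based on novel developments in the field of cancer immune profiling".

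**The concern.** A triple-negative tumor cannot meet Section 3.1.2, so the data that Assay 3 calls TNBC will not exist in this trial. The reference subset is defined by the absence of the receptors that every participant must have.

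The choice of reference matters because normalization comes before classification. Aligning two cohorts gene by gene assumes that their average difference is technical. Here part of that difference is biological: it is the hormone-receptor signal that separates luminal from non-luminal tumors. Removing it could move luminal tumors toward a non-luminal call. The calls then enter models for response, so errors made at this step would carry into any reported association.

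**Working it through.** **1. Is there a figure to reproduce?** No. The plan gives no sample size, power or error rate for this step. The mismatch is textual: Section 3.1.2 admits only HR-positive disease, while Assay 3 normalizes to a receptor-negative subset.

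**2. Does another section correct it?** No. Section 13.7.2 covers transcript abundance, differential expression, pathways and immune signatures from RNA-seq. It mentions neither PAM50 nor a reference subset. Section 13.7.1 does not mention them either. No section limits the step to a triple-negative subgroup.

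**3. What does the reference do to the calls?** All inputs here are assumptions, because the documents give none. Take two classes, luminal-like and basal-like, whose gene means are +e and −e in the direction of a luminal-versus-basal contrast. Let p_T be the luminal-like share in the trial and p_R the share in the reference. Aligning gene-wise means gives a luminal-like sample the expected signal

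 e·[1 − (2p_T − 1) + (2p_R − 1)] = e·[1 + 2(p_R − p_T)].

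With a matched reference (p_R = p_T) the factor is 1 and the signal is intact. With p_T = 0.95 and p_R = 0.10 it is 1 + 2(0.10 − 0.95) = −0.70, so the sign reverses and the sample is called basal-like. A single constant applied to all genes leaves the contrasts between genes within a sample unchanged, so it does not alter the call.

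**4. Illustrative simulation.** There were 50 genes (25 up and 25 down in luminal-like tumors), unit noise SD, 110 trial samples with a random gene-wise platform shift, a TNBC reference of 150, a matched reference of 600, and 200 replicates per scenario. Gene-wise alignment used medians. The last two columns give the percentage of trial samples misclassified after alignment to the TNBC reference.

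| p_T | p_R | Factor 1 + 2(p_R − p_T) | e = 0.5 | e = 1.0 |
|---|---|---|---|---|
| 0.95 | 0.10 | −0.70 | 94 | 95 |
| 0.95 | 0.20 | −0.50 | 92 | 95 |
| 0.95 | 0.30 | −0.30 | 83 | 94 |
| 0.85 | 0.10 | −0.50 | 82 | 85 |
| 0.85 | 0.20 | −0.30 | 75 | 85 |
| 0.85 | 0.30 | −0.10 | 59 | 81 |
| 0.70 | 0.10 | −0.20 | 54 | 69 |
| 0.70 | 0.20 | 0.00 | 42 | 62 |
| 0.70 | 0.30 | +0.20 | 22 | 40 |

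In every scenario the matched reference gave about 0% misclassified and the single scalar gave 0% to 1%. The factor is for means; medians lie closer to the majority class, which raises the error in the lower rows. The matched reference was drawn with the trial's own class mix, which is the most favorable case for it.

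**5. How many samples?** The enrollment of 110 is a ceiling on baseline samples. Biopsy depends on safe access. Lung core and bone biopsies are not done unless clinically indicated (Section 9.2.2), while bone-only disease is eligible (Section 3.1.4). An inadequate biopsy need not be repeated. On-treatment pairs are planned for at least the first 27 accessible patients per arm, with 24 expected to be evaluable (Section 13.7.1). RNA analysis itself is optional, and NanoString signatures may replace whole-transcriptome sequencing.

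**The case against.** The strongest reply is that the documents do not establish harm. The plan says only that the normalization is global. That word does not favor a gene-wise method, and under one common scalar the calls barely change. Every simulation input is assumed, only two classes were modeled, and how PAM50 responds to a reference set is described in cited papers that are not part of the documents. This stands: misclassification is conditional. A reader might infer that subtype is certain to be wrong for every patient and that the response associations would be meaningless; the text does not support either step.

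The second reply concerns weight. The assay is listed as potential, all tissue biomarker work is exploratory, no objective in Section 1.4 names intrinsic subtype, and Section 13.7 contains no subtype analysis. This also stands, and it limits how much the point matters.

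The third reply is that Section 9.7 and the allowance in Assay 3 for current methods already permit a change. This does not answer the point. Section 9.7 is tied to developments in the field, and the receptor status of the enrolled patients is not one. Nothing in either clause replaces the stated reference. Leaving the choice until response is known would add analyst discretion to the association tests.

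A reader might also infer that the paragraph was carried over from a TNBC protocol. Three mentions make that plausible, but no section says so, and the point does not need it.

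**Conclusion.** The point holds in conditional form. As written, Assay 3 labels the data, justifies the analysis and chooses the reference for a population that the trial excludes. That part is certain from the text.

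The consequence is not certain. Under gene-wise alignment many calls could be wrong: 22% to 95% in the simulation, given a trial that is 70% to 95% luminal-like and a TNBC reference that is 10% to 30% luminal-like. Under a single scalar the effect is about 0% to 1%. These figures show direction and sensitivity and are not estimates for this trial.

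It would be tempting to say that 110 baseline samples plus the on-treatment samples are affected. The documents support only a smaller, unstated number: those biopsied, adequate and RNA-sequenced. Primary and secondary endpoints, sample size and decision rules are unaffected. The paragraph should be corrected, but the error does not threaten the trial's main conclusions.

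**What to change.** Rewrite the subtyping paragraph in Section 9.3.3 (Assay 3):

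1. Correct all three TNBC mentions: the rationale sentence, the description of the study data, and the reference subset. Changing only the last two would leave a TNBC rationale attached to an HR+/HER2- analysis.
2. Name the HR+/HER2- subset of the same TCGA data as the reference, or another reference with a stated and comparable ER mix. The mix deserves a sentence, because the trial admits ER from 1% and separates 1-9% from 10% or greater in its Cox models (Section 13.5).
3. State whether normalization is gene-wise or sample-wise, and fix this before subtype calls are tested against response.

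The cost is an edit to one paragraph. It needs no new samples or assays, and the classification pipeline stays the same.

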9.3.4 Sites Performing Correlative Studies and/or Data Analysis

De-identified biospecimens and data may be shared with the following entities for the purposes described above:

DFCI Breast Translational Hub-Smith (T-Hub)
DFCI Center for Immuno-Oncology
DFCI Core Blood and Tissue Bank
The Broad Institute of MIT
Nanostring Technologies, Inc
Brigham and Women's Hospital (including Center for Advanced Molecular Diagnostics)
Harvard Medical School
Yale Cancer Center
Adaptive Biotechnologies
Foundation Medicine, Inc.
Discovery Life Sciences/Qualtek
Reveal Genomics
BostonGene
[REDACTED]

Ventana

9.4 Blood Collection

Research blood collection is mandatory for all patients for flow cytometry of PBMCs and potential DNA isolation. The samples will be banked in the DFCI Breast Translational Hub-Smith (T-Hub) for these and future research purposes. These specimens will become the property of the DF/HCC.

The following research blood samples are required:

Cycle 1 Day 1:

- 2 lavender top tubes (10 mL) for whole blood
- 2 Streck tubes (10 mL) for whole blood
- 2 CPT tubes (8 mL each) for whole blood

With Restaging (Every 9 weeks, coinciding with Day 1 of that cycle):

- 2 Streck tubes (10 mL) for whole blood
- 2 CPT tubes (8 mL each) for whole blood

Off Treatment (with or without progressive disease):

- 2 Streck tubes (10 mL) for whole blood
- 2 CPT tubes (8 mL each) for whole blood

The following research blood samples are optional for patients who come off treatment for a reason other than progressive disease until progressive disease, start of another anti-cancer therapy, or death:

Follow Up (every 9-12 weeks):

- 2 Streck tubes (10 mL) for whole blood
- 2 CPT tubes (8 mL each) for whole blood

If sample collection is missed at baseline or at the time of progression, then the sample should be drawn at a future appointment before starting another anti-cancer therapy if possible.

For retreatment patients the following research blood samples are required:

With Restaging (Every 9 weeks, coinciding with Day 1 of that cycle):

- 2 Streck tubes (10 mL) for whole blood
- 2 CPT tubes (8 mL each) for whole blood

End of Treatment (with or without progressive disease):

- 2 Streck tubes (10 mL) for whole blood
- 2 CPT tubes (8 mL each) for whole blood

